4.5 Study Safety Assessments

4.5.1 Incidence and Severity of Adverse Events:

Following the first laser treatment, adverse device effects (ADEs) will be assessed post-treatment and at each subsequent subject visit using the following scale:

- 1= mild: requires minimal or no treatment and does not interfere with the Subject's daily activities.
- 2= moderate: may cause some interference with functioning.
- 3= severe: interrupts Subject's usual daily activity and may require treatment.

4.5.2 Treatment-related Discomfort

Subjects will be asked to rate the average amount of discomfort experienced during laser treatment using the Pain Rating Scale found in Appendix 2.

4.6 Photographs

Standardized digital photographs will be taken of each subject's face at baseline, prior to all laser treatments and at both follow-up visits. Any jewelry will be removed from the area being photographed. Hair will be pulled away from the face with a headband and subject will have recently cleansed skin. Facial photographs will be obtained from 3 angles: with the subject facing forward, 45° to the right and 45° to the left. Photographs will be taken in the same windowless room equipped with adequate lighting. The room lighting, camera positioning and subject positioning should be consistent for all study visit photographs. Digital camera settings should remain the same for all photographs and the highest resolution settings should be utilized.

4.7 Study Discontinuation

The sponsor (Cutera, Inc.) has the right to terminate this study at any time. Reasons for terminating the study may include, but are not limited to, the following: incidence or severity of adverse events in this or other studies indicates a potential health hazard to subjects; subject enrollment is unsatisfactory; number of protocol deviations is unacceptable; data recording is inaccurate or incomplete; or questionable study site compliance with ICH-E6, Good Clinical Practice.

4.8 Investigator Selection

The Investigator will be invited to participate in the study based on his/her medical specialty, experience conducting clinical research studies and experience in the use of light-based devices for aesthetic indications. Access to potential study subjects and the Investigator's sincere interest in this study along with expressed willingness to cooperate with the study process and requirements will also be considered.

5 STUDY POPULATION

5.1 Study Subject Recruitment and Selection

Twenty male or female subjects, ages 35 to 55, with Fitzpatrick Skin Type I-IV (see Appendix 4 for skin type classification) who desire laser treatment for facial wrinkles or photo-rejuvenation will be studied. Subjects will be recruited to participate from the local population. Subjects may also be recruited from the Investigator's existing patient database or from patients who present themselves to the study site requesting treatment. Only subjects who meet all eligibility criteria and who provide written informed consent will be enrolled into the study.

Each subject will be evaluated by the Investigator to assess his/her suitability for entry into the study according to the following inclusion and exclusion criteria.

5.1.1 Inclusion Criteria

To be included in the study, subjects must meet all of the following Inclusion Criteria:

1.	Female or Male, 35 to 55 years of age (inclusive).
2.	Fitzpatrick Skin Type I – IV (Appendix 4).
3.	Desires non-invasive and non-ablative treatment of skin-aging or photo-rejuvenation of the skin.
4.	Have signs of moderate skin aging, including presence of mild to moderate rhytides around eyes and upper lip, multiple lentigines, diffuse erythema or telangiectasia, and a score between 4 and 7 (inclusive) on the Fitzpatrick Wrinkle Classification Scale (Appendix 3).
5.	Subject must be able to read, understand and sign the Informed Consent Form.
6.	Must be willing and able to adhere to the treatment and follow-up schedule and post-treatment care instructions.
7.	Willing to have very limited sun exposure and use an approved sunscreen of SPF 30 or higher on the treatment area every day for the duration of the study, including the follow-up period.
8.	Willing to have digital photographs taken of the treatment area and agree to use of photographs for presentation, educational or marketing purposes.

9.	Agree to not undergo any other procedure(s) for skin rejuvenation during the study, including but not limited to chemical peel, laser and light based device treatment, and home-use device treatment.
10.	Agree to not undergo any injection of botulinum toxin, collagen, hyaluronic acid filler or other dermal filler during the study.
11.	Post-menopausal or surgically sterilized, or using a medically acceptable form of birth control at least 3 months prior to enrollment and during the entire course of the study, and no plans to become pregnant or to father a child for the duration of the study.

5.1.2 Exclusion Criteria

Subjects will be excluded from the study if they meet any of the following Exclusion Criteria:

1.	Participation in a clinical trial of another device or drug within 6 months prior to enrollment or during the study.
2.	Any type of prior cosmetic treatment to the target area within 6 months of study participation, such as laser or light-based procedures or surgery.
3.	Prior injection to the face of botulinum toxin, collagen, hyaluronic acid filler or other dermal filler within 6 months of study participation, as applicable.
4.	Systemic use of retinoid, such as isotretinoin, or corticosteroid, as applicable, within 6 months of study participation.
5.	Use of topical medications on the face, such as antibiotics, benzoyl peroxide, retinoids (isotretinoin), corticosteroids, hydroquinone, or products containing dihydroxyacetone or alpha-hydroxy with concentration > 8%, within 1 month of participation.
6.	History of malignant tumors in the target area.
7.	Skin abnormalities in the target area, e.g., cuts, scrapes, wounds, scars, large moles.
8.	Pregnant and/or breastfeeding.
9.	Having an infection, dermatitis or a rash in the treatment area.
10.	Significant concurrent illness, such as diabetes mellitus or cardiovascular disease, e.g., uncontrolled hypertension.
11.	Suffering from coagulation disorders, or taking prescription anticoagulation medication which might make study participation unsafe according to Investigator's discretion.
12.	History of keloid scarring, hypertrophic scarring or of abnormal wound healing.
13.	History of immunosuppression/immune deficiency disorders or currently using immunosuppressive medications.
14.	History of vitiligo, eczema, or psoriasis.
15.	History of connective tissue disease, such as systemic lupus erythematosus or scleroderma.
16.	History of seizure disorders due to light.
17.	Any use of medication that is known to increase sensitivity to light according to Investigator's discretion.
18.	History of disease stimulated by heat, such as recurrent herpes simplex and/or herpes zoster (shingles) in the treatment area, unless treatment is conducted following a prophylactic regimen

19.	History of radiation to the treatment area or undergoing systemic chemotherapy for the treatment of cancer.
20.	History of pigmentary disorders, particularly tendency for hyper- or hypo-pigmentation.
21.	Anytime in life, having have used gold therapy (gold salts) for disorders such as rheumatologic disease or lupus.
22.	Excessively tanned in areas to be treated or unable/unlikely to refrain from tanning during the study.
23.	Current smoker or history of smoking within 6 months of study participation.
24.	As per the Investigator's discretion, any physical or mental condition which might make it unsafe for the subject to participate in this study.

5.2 Subject Numbering

If a subject meets the study eligibility criteria and is willing to participate, the subject will be assigned a study subject identification number. This number is comprised of a sequential subject number and the subject initials (first and last names).

5.3 Subject Discontinuation Criteria

If possible, every subject should remain in the study until completion of the required follow-up period. However, participation in this study is completely voluntary and a subject can choose to withdraw from the study at any time. Decision to withdraw will not affect or prejudice the subject's continued medical care in any way. In those instances, the investigator will attempt to obtain a final clinical assessment and an adverse device effect evaluation for the subject prior to this withdrawal. A subject will be considered lost to follow-up only after three unsuccessful, documented attempts to contact the subject have been made.

In addition, a subject can be discontinued for any of the following reasons: the Principal Investigator decides that continuing in the study would not be in the subject's best interest, a subject is noncompliant with the protocol, a subject has a serious reaction to the treatment, a subject develops any of the exclusion criteria during the study period or the study is stopped by the study sponsor.

6 [REDACTED]

[REDACTED]

[REDACTED]

[REDACTED]

[figure not shown]
[REDACTED]

[REDACTED]

[REDACTED]

6.2

A large black rectangular redaction box covers the majority of the page content, starting below the header and ending above the footer. The redaction is not perfectly uniform, with some white space visible at the top and bottom edges.

7 ADVERSE DEVICE EFFECTS

7.1 Definitions

[REDACTED]

[REDACTED]

7.2 Recording ADEs and SADEs

All ADEs/SADEs will be: (1) evaluated and must be recorded in the subject's medical chart and in the study case report forms (CRFs); (2) monitored and tracked from the time of the first treatment with the Cutera ExcelV laser system.

At each contact with the subject, the investigator must seek information on ADEs/SADEs by specific questioning and, as appropriate, by examination. ADEs/SADEs may be observed by the investigator and/or clinical research staff, elicited from the subject and/or family member or volunteered by the subject. All observed and volunteered adverse signs and symptoms, anticipated or unanticipated, regardless of severity or frequency, will be recorded in the case histories (medical chart and CRFs). Included in the description should be the nature of the sign or symptom, the date of onset, date of resolution (duration), the severity, anticipated or unanticipated, the relationship to study treatment or other therapy, the action taken (if any), and the outcome.

All SADEs, anticipated or unanticipated, must be reported to Cutera immediately but not later than 5 working days. The SADE must be recorded in: (1) the AE CRF and (2) a written report must be submitted to Cutera within five (5) working days after the investigator first learns of the event and is to include a full description of the event and sequelae, in the format detailed by the Cutera Serious Adverse Device Effect Form.

7.3 Follow-up of Subjects after ADEs and SADEs:

All reported ADEs/SADEs should be followed until resolution or until the subject's participation in the study ends. Resolutions of ADEs/SADEs are to be documented on the appropriate CRFs. All ADEs that result in permanent discontinuation from this clinical trial, whether serious or not, should also be reported on the subject Non-Completion of Study Form.

8 POTENTIAL RISKS / BENEFITS

[REDACTED]	[REDACTED]	[REDACTED]	[REDACTED]
[REDACTED]	[REDACTED]	[REDACTED]	[REDACTED]
[REDACTED]	[REDACTED]	[REDACTED]	[REDACTED]
[REDACTED]	[REDACTED]	[REDACTED]	[REDACTED]
[REDACTED]	[REDACTED]	[REDACTED]	[REDACTED]

For more information, contact the Office of the Vice President for Research and the Office of the Vice President for Student Affairs.

© 2019 Pearson Education, Inc.

8.2 Potential Benefits

The subjects may or may not benefit from the treatment with the study device. Potential benefit of laser treatment for photo-rejuvenation is improved appearance of skin, diminished appearance of rhytides, improvement in telangiectasia and lightening of lentigines. There is no guarantee of success.

9 RISK MANAGEMENT

The investigator participating in this study was chosen based on extensive and safe experience with the use of lasers in dermatology applications. This is the most critical element in managing subject risk. In addition, study investigators will be trained on the use of the Cutera excelV laser system by a representative of Cutera.

10 DATA ANALYSIS PLAN

10.1 Sample Size

Up to [REDACTED] subjects will be enrolled in this safety and efficacy study.

10.2 Demographics and Subject Characteristics at Baseline

Subject demographics, medical history, concomitant medications will be tabulated and summarized descriptively.

10.3 Statistical Analysis Methods

10.3.1 Analysis Sets

The efficacy analysis set will include all subjects who received at least one laser treatment session and complete a follow-up visit. The safety analysis set will include all subjects enrolled in the study who had at least one laser treatment session.

Missing data will not be imputed for efficacy or safety endpoints.

10.3.2 Analysis of Primary Endpoint

Formal statistical analysis is not planned for this study. The primary efficacy endpoint data, blinded reviewer degree of improvement at 12 weeks post-final treatment, will be summarized descriptively.

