4 STUDY DESIGN

This is a single-center prospective, open-label uncontrolled study in 15 male or female subjects, age 35 to 55 years who desire non-ablative laser treatment for facial photo-rejuvenation, specifically improvement of rhytides, lentigines, erythema, telangiectasia and skin texture. Subjects will receive [REDACTED] laser treatments [REDACTED] and complete [REDACTED] follow-up visits; [REDACTED] at 12 weeks post-final treatment.

[REDACTED]

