4.3 Study Effectiveness Assessments

4.3.1 Blinded Assessments

4.3.1.1 Blinded Reviewer's Global Assessment of Improvement

Independent, blinded physician reviewers will be asked to perform an assessment of subject photographs at baseline, [REDACTED] and 12 weeks post-final treatment. The arrangement of each subject's pair of baseline and

post-final treatment photographs will be randomized such that the baseline photograph will be randomly assigned to the left or right side of the page. The order of subject photograph pairs will also be randomized. The reviewers will be blinded to the treatment parameters used, the subject data, the temporal order of photographs (before and after), and follow-up time point.

The reviewers will be asked to first determine the temporal order of each photograph pair, then rate the degree of improvement observed in the post-treatment photograph using the Physician's Global Assessment of Improvement Scale:

4 = Very Significant Improvement [REDACTED]

3 = Significant Improvement [REDACTED]

2 = Moderate Improvement [REDACTED]

1 = Mild Improvement [REDACTED]

0 = No Change [REDACTED]

4.3.1.2 [REDACTED]

4.3.2 [REDACTED]

[REDACTED] [REDACTED]

[REDACTED] [REDACTED]

[REDACTED]

[REDACTED]

4.3.3.2 [REDACTED]

[REDACTED]

[REDACTED]

[REDACTED]

[REDACTED]

4.4 [REDACTED]

[REDACTED]

[REDACTED]

[REDACTED]

[REDACTED]

[REDACTED]

[REDACTED]

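### The blinded before/after call has a chance value of 50% fixed by design, but the plan never reports it; pre-specifying it with an exact interval would be a cheap improvement

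*Combined protocol and SAP*

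**What the plan says.** Section 4 describes the trial thus: "This is a single-center prospective, open-label uncontrolled study in 15 male or female subjects". Section 3 makes evaluation of efficacy one of two objectives.

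Section 4.3.1.1 sets up the photographic reading. Within each pair, "the baseline photograph will be randomly assigned to the left or right side of the page". Readers are masked to several things, including "the temporal order of photographs (before and after), and follow-up time point". The order call comes before the grade: "The reviewers will be asked to first determine the temporal order of each photograph pair". The grade then runs from 4 down to 0, where 0 means no change.

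Section 10.3.2 covers the primary endpoint in two sentences. The first is "Formal statistical analysis is not planned for this study". The second says that the "blinded reviewer degree of improvement at 12 weeks post-final treatment, will be summarized descriptively". The order call is not mentioned there or anywhere else in the visible text after section 4.3.1.1.

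**The concern.** The primary grade has no built-in reference value. It cannot go below 0, so if nothing changed, reading noise can only raise its average. There is no control group to show how large that rise would be, and no success threshold is visible. A descriptive distribution of grades therefore leaves the reader to judge unaided how much of it reflects real change.

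The order call is different. Because placement is randomised and the reader is masked to it, the proportion expected to be right under no visible change is known in advance. The protocol collects this information for every pair and gives it no visible use. If it is not pre-specified, it may go unreported, or be reported only when it looks favourable.

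**Working it through.** **Inputs from the documents**
- Enrolment: 15 (Protocol Summary and section 4) or twenty (section 5.1). The figure in section 10.1 is redacted. Both sizes are worked below.
- Readers: more than one, number not visible (section 4.3.1.1).
- Missing data: not imputed (section 10.3.1). No dropout rate is visible.

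**Assumptions not in the documents**
- Left and right are equally likely, so the chance value is 0.5. Section 4.3.1.1 implies this but does not state it.
- One-sided level 0.025, which matches a two-sided 95% interval.
- True shares correctly ordered of 70%, 80% and 90%, as illustrations.

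The plan gives no significance level, power or threshold for this measure, so there is no figure of its own to reproduce.

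**Step 1: how many correct calls exclude chance.** With one call per subject, P(X ≥ r) = Σ C(n,k) / 2ⁿ for k = r to n.
- n = 15, r = 12: (455 + 105 + 15 + 1) / 32,768 = 576 / 32,768 = 0.0176. Clopper-Pearson 95% interval for 12/15: 51.9% to 95.7%.
- n = 15, r = 11: (1,365 + 576) / 32,768 = 0.0592. Interval for 11/15: 44.9% to 92.2%.
- n = 20, r = 15: 21,700 / 1,048,576 = 0.0207. Interval for 15/20: 50.9% to 91.3%.
- n = 20, r = 14: 60,460 / 1,048,576 = 0.0577. Interval for 14/20: 45.7% to 88.1%.

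The cut is 12 of 15 or 15 of 20. In each case the lower 95% limit passes 50% exactly where the one-sided p-value falls to 0.025 or below, so the interval alone carries the test.

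**Step 2: power.** Power = Σ C(n,k) pᵏ (1−p)ⁿ⁻ᵏ for k = r to n. For n = 15, r = 12, p = 0.8: 0.250 + 0.231 + 0.132 + 0.035 = 0.648.

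| Evaluable subjects | Cut | True share 70% | 80% | 90% |
|---|---|---|---|---|
| 12 | 10 | 25.3% | 55.8% | 88.9% |
| 15 | 12 | 29.7% | 64.8% | 94.4% |
| 20 | 15 | 41.6% | 80.4% | 98.9% |

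The row for 12 shows the effect of losing three of 15 subjects.

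**Step 3: why one call per subject.** Suppose calls are pooled as if independent while the readers always agree.
- Two readers: the nominal 0.025 cut is 21 of 30. It is met when at least 11 of 15 subjects are ordered correctly, so the true error is 5.9%.
- Three readers: the cut is 30 of 45. It is met when at least 10 of 15 are correct, so the true error is (3,003 + 1,941) / 32,768 = 15.1%.

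A majority call across an odd number of readers keeps the 50% value, because it is still a single left/right choice made without knowledge of the placement. With an even number, counting a tie as incorrect pulls the no-change value below 50% (to 0.5 × 0.5 = 25% for two readers guessing independently), so the comparison with 50% errs on the cautious side.

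**The case against.** The strongest reply is that a purely descriptive analysis is an acceptable and openly stated choice for a small, single-arm study. No visible hypothesis, threshold or power claim conflicts with it. That stands: nothing here is a contradiction or a wrong figure. But a descriptive plan can still report a proportion and its interval, so the choice does not explain leaving the order call out.

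Three further points stand as limits.
- A reader might infer that the trial gives up its only possible test of efficacy. The documents do not support that. The contents list a blinded photoaging assessment (4.3.1.2) and analyses of secondary endpoints (10.3.3), and the text of neither is readable. The claim holds for the visible text only.
- A reader might infer that correct ordering above chance would show that the laser improved the skin. It would not. Section 5.1.1 requires limited sun exposure and daily sunscreen, section 5.1.2 excludes several topical products within one month of participation, and photographic conditions can drift. Any of these could make the photographs distinguishable.
- The 50% value is not guaranteed. Section 4.6 calls for photographs at both follow-up visits, and section 4.3.1.1 lists a redacted assessment point besides baseline and 12 weeks. If one baseline photograph appears in two pairs, a reader who recognises it could infer the order without any skin change. Whether pairs are shown this way is not visible.

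It is also fair to say that power at 15 subjects is modest, and that masking to order already limits expectation bias in the grades.

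**Conclusion.** The point holds as a low-cost improvement. In the visible text, the order call is the only efficacy measure whose no-change value is fixed by design, and section 10.3.2 makes no use of it. Reporting it would give an uncontrolled trial, with a grade that cannot fall below zero, one reference value that it otherwise lacks.

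The analysis can succeed or fail at the stated sizes: 12 of 15 or 15 of 20 would exclude 50%, while 11 of 15 would not. A result near 50% would caution against reading the grades as improvement. At n = 15 it would not prove absence of effect, since power is about 30% at an assumed true share of 70% and 65% at 80%.

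These figures assume equal-probability placement, one call per subject, a 12-week pair for every subject counted, and no clue to order from a repeated baseline photograph.

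**What to change.** Add to section 10.3.2, before any photographs are read:
- The proportion of evaluable subjects whose 12-week pair is correctly ordered, with an exact Clopper-Pearson 95% interval read against 50%. State that this is equivalent to a one-sided exact test at 0.025.
- One call per subject: the majority across readers, with a stated tie rule (for example, a tie counts as incorrect). Show each reader separately and do not pool readers as independent.
- Confirmation that left/right placement is made with equal probability.
- If a baseline photograph appears in more than one pair, use a reading in which the 12-week pair cannot be identified from the repeated image, or state that the 50% reference may not hold.
- The interpretation: a result above 50% shows only that before and after photographs can be told apart, and at n = 15 a result not distinguishable from 50% does not prove no effect.

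Report the 0-4 grades beside it. Reconcile the enrolment figures of 15 (section 4) and twenty (section 5.1), because the cut depends on them.

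The cost is a short paragraph, with no new visits. Data already being collected suffice, unless repeated baseline photographs make a separate reading of the 12-week pairs necessary. The downside for the sponsor is that the trial may have to report a result not distinguishable from chance.

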10.3.4 Safety Analyses

Safety variables will be analyzed descriptively.

The safety variables for this study are:

1. Subject discomfort (pain) during treatment (to be descriptively displayed).

2. Incidence and severity of adverse effects during study duration (to be displayed descriptively as counts and frequency distributions).

Enrolled subjects who received at least one treatment will be included in the safety analyses. Device-related and procedure-related adverse effects (AEs) and subjects who prematurely terminate from the study due to an adverse device effect, including the treatment-related pain ratings, as reported on case report forms will be tabulated and analyzed. For a given AE term, counting will be done by subject, not by event, i.e. for a subject reporting the same AE more than once, the event will be counted only once, at the most severe and most-related occurrence. The number and percentage of subjects experiencing each AE Term will be descriptively summarized. Statistical hypothesis testing will not be performed for safety data.

11 [REDACTED]

[REDACTED]

[REDACTED]

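### Section 10.3.4 specifies tables only for device- and procedure-related effects, although section 7.2 records all adverse signs and symptoms; an all-event table is needed

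*Combined protocol and SAP*

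**What the plan says.** Section 7.2 (Recording ADEs and SADEs) sets the scope of collection: "All observed and volunteered adverse signs and symptoms, anticipated or unanticipated, regardless of severity or frequency, will be recorded in the case histories", meaning the chart and the CRFs. The description of each event includes "the relationship to study treatment or other therapy, the action taken (if any), and the outcome". The form therefore allows for events put down to something other than the laser.

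Section 10.3.4 (Safety Analyses) sets the scope of reporting, in two places that do not match. Its list of safety variables has, as item 2, "Incidence and severity of adverse effects during study duration", with no condition on relationship. The sentence that says what will be tabulated is narrower. It names "Device-related and procedure-related adverse effects (AEs", and adds subjects who leave early because of an adverse device effect. The abbreviation is introduced there for the related effects. The rule that counts each subject once per term, and the summary of numbers and percentages of subjects per term, then use that abbreviation.

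Section 4.1.2 defines the safety endpoint as adverse device effects, including pain during treatment. The protocol summary and section 4 describe an open-label study without a control group. Section 10.3.4 rules out hypothesis testing of safety data.

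**The concern.** Safety is the first objective in section 3, and with no test planned the descriptive tables are the safety result. If they hold only events judged related to device or procedure, the reported incidence is the joint product of what happened and how it was attributed. In a controlled trial, the rate of all events in the other arm gives some check on attribution. Here there is none, and everyone knows that every subject was treated. The blinding in section 4.3.1.1 covers only the photograph review.

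The stake is transparency. A reader of the planned tables could not tell how many recorded events were set aside as unrelated, or what they were. An analyst could also follow either item 2 or the tabulation sentence, produce different tables, and claim to have followed the plan in both cases.

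**Working it through.** The plan states no safety incidence or precision, so it has no figure of its own to reproduce. The check has two parts.

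**Scope, step by step**

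1. Recorded (section 7.2): all adverse signs and symptoms, each with a relationship.
2. Listed as a safety variable (section 10.3.4, item 2): adverse effects over the study, no relatedness condition.
3. Named for tabulation (section 10.3.4): related effects, plus subjects who leave because of an adverse device effect.
4. Counted and summarised by term (section 10.3.4): events under the abbreviation defined in step 3.

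Steps 1 and 2 include an event attributed to other therapy. Steps 3 and 4 leave it out.

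**Size**

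Inputs: N = 15 (protocol summary and section 4) or N = 20 (section 5.1); the number in section 10.1 is redacted. Both are carried, on the assumption that every enrolled subject is treated and so enters the safety set of section 10.3.1. Counting is by subject, at the most severe and most related occurrence. A subject therefore drops out of a term only if all of that subject's occurrences of it are judged unrelated.

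Let k be the subjects with a given term and u those who drop out in this way. The displayed incidence is (k − u)/N instead of k/N, a difference of u/N. For u = 1 this is 1/15 = 6.7 points or 1/20 = 5.0 points.

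The documents give neither k nor u. As an illustration, assume k = 4 and let u run over its whole range. The exact (Clopper-Pearson) two-sided 95% intervals show scale only.

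| u | N = 15: displayed (95% CI) | N = 20: displayed (95% CI) |
|---|---|---|
| 0 | 4/15 = 26.7% (7.8 to 55.1) | 4/20 = 20.0% (5.7 to 43.7) |
| 1 | 3/15 = 20.0% (4.3 to 48.1) | 3/20 = 15.0% (3.2 to 37.9) |
| 2 | 2/15 = 13.3% (1.7 to 40.5) | 2/20 = 10.0% (1.2 to 31.7) |
| 3 | 1/15 = 6.7% (0.2 to 31.9) | 1/20 = 5.0% (0.1 to 24.9) |
| 4 | 0/15 = 0% (0 to 21.8) | 0/20 = 0% (0 to 16.8) |

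The same recorded data can thus be displayed as anything from 0% to 26.7% (N = 15) or 0% to 20.0% (N = 20), depending only on attribution. The intervals overlap heavily, as they must at this size. The table shows how sensitive the display is; it does not predict what will happen.

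**The case against.** The strongest reply is that the tabulation matches the endpoint. Section 4.1.2 names adverse device effects, so attribution is built in, and in a small descriptive study an all-event table is a supplement. That stands as far as the endpoint goes, and the endpoint should stay as named. It does not explain why events recorded under section 7.2 should have no planned display.

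Second, section 10.3.4 never says that only related effects are tabulated. Item 2 is unrestricted, and counting at the most related occurrence suggests that grades of relationship are carried into the analysis. This is why the point is put as the natural reading together with an inconsistency, and not as an explicit exclusion. The counting rule does not settle it. It chooses among repeats of one term in one subject and makes no provision for a term judged wholly unrelated.

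Third, section 7.2 is headed for device effects, so its recording sentence might be meant for those alone. Its wording is broader than that, and its relationship item provides for other therapy.

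A reader might also infer three stronger things that the documents do not support:

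- *That attribution cannot be verified.* Relationship is recorded in chart and CRF, so the full set of events is recoverable by whoever holds the data. Only the reader of the planned tables cannot see it.
- *That an unblinded investigator alone decides relatedness.* Section 7.2 says that "the investigator must seek information on ADEs/SADEs by specific questioning and, as appropriate, by examination", but the visible text does not say who assigns relationship or whether it is reviewed. The definitions in section 7.1 are redacted and may cover this.
- *That the incidence of device effects will be biased downward.* A subset cannot exceed the whole, but that is all the arithmetic shows. With every subject treated, coincidental events could equally be over-attributed to the laser.

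**Conclusion.** The point holds as a gap in the planned display and an inconsistency within section 10.3.4. Collection covers all adverse signs and symptoms, tabulation is specified only for related ones, and one line of the same section says otherwise. Each subject affected moves a term by 6.7 points at N = 15 or 5.0 points at N = 20. The number of such subjects is unknown and may be zero.

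The conclusion rests on reading the abbreviation as it is defined in the tabulation sentence, and on the visible text alone. It does not show that any result will be wrong. The conflict between 15 and 20 subjects is a separate matter and affects only the denominator here. The change should be made because it is cheap and, with no control group and no safety test, these tables carry the safety conclusion.

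**What to change.** In section 10.3.4:

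- Tabulate all adverse signs and symptoms recorded from first treatment to last visit, by subject, term and maximum severity, whatever the attributed relationship.
- Show device- or procedure-related events as a labelled subset of that table.
- Define the abbreviation for adverse effects once, and make item 2 and the tabulation sentence refer to the same set.
- Keep the adverse device effect endpoint in section 4.1.2 as named.

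The cost is one extra descriptive table from data already on the CRF, with no new visits, assessments or subjects. The downside is that displayed incidence may look slightly higher because unrelated events are shown; the labelled subset keeps the endpoint figure visible next to it.
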